7.5 SAE Reporting and Timeframe

Reporting requirements will comply with all EU safety reporting requirements as detailed in current legislation and all applicable local regulations for safety reporting.

The investigator or investigator's team will report all protocol defined SAEs and ECIs to the Sponsor (MedSIR) no later than 24 hours of any site study team staff becoming aware of the event as follows:

- The full details of the SAE and/or ECI should be collected and fully documented using the SAE form and sent to the Sponsor (MedSIR).
- Follow-up information, copies of any relevant test results, event outcome and the opinion of the investigator as to the relationship between the IMP and the SAE and ECI, accompanied by other applicable documentation when it is requested, will be sent along with the SAE form, if available on the day the event is reported or as soon as possible if it is not.
- The original SAE reporting form and the confirmation from the Sponsor must be kept with the CRF documentation at the study site(s).

All SAE forms will be sent by the investigator or investigator's team to the Sponsor (MedSIR) according to the reporting instructions provided by MedSIR at the site initiation visit and filed in the Investigator's File.

SAEs and ECIs will be followed until resolved, a stable outcome is reached, subject/patient is lost to follow-up, or dies.

As sponsor, MedSIR will be responsible for ensuring that events are reported within the mandated timeframe to the European Medicines Agency (EMA), other competent authorities, Institutional Review Boards (IRBs)/ECs, and investigator(s), as necessary and in accordance with all applicable guidelines, approved directives and regulations. All safety reporting local regulatory requirements will be followed.

7.6 Expedited reporting to HAs, investigators, IRBs, and ECs

To determine reporting requirements for single SAE cases, MedSIR (as Sponsor) or its designee will assess the expectedness of these events using the following reference documents:

- INCMGA00012 (retifanlimab) IB.

MedSIR (as Sponsor) or its designee will compare the severity of each event and the cumulative event frequency reported for the study with the severity and frequency reported in the applicable reference document.

Reporting requirements will also be based on the investigator's assessment of causality and seriousness, with allowance for upgrading by the Sponsor as needed.

Within seven calendar days after being notified of the event, MedSIR (as Sponsor) or its designee will report unexpected fatal or life-threatening events associated with the use of the study drug to the regulatory agencies and competent authorities, to the investigators and Ethics Committees (ECs). MedSIR (as Sponsor) or its designee will report other unexpected SAEs associated with the use of the study medication to the appropriate competent authorities (according to local guidelines), investigators, and ECs by a written safety report within 15 calendar days of notification. All safety expedited reports will be reported in accordance with all regulatory reporting obligations (including timelines) and local regulatory requirements.

7.7 Other Safety-Related Reports

As Sponsor, MedSIR will assess constantly the benefit/risk rate of the trial that means a continuous evaluation of the safety profile of the drugs under investigation will be done using all available information. MedSIR will provide the regulatory agencies and competent authorities and the investigators with any relevant information that may affect the benefit/risk rate of the trial. An annual DSUR safety report for study INCMGA00012 (retifanlimab) will be prepared and distributed by MedSIR or its designee in accordance with all regulatory reporting obligations and local regulatory requirements.

In order to ensure the correct and necessary exchange of safety related information between MedSIR (as Sponsor) and Incyte a contract will be established and signed between MedSIR and these companies.

MedSIR or its designee will report any finding of noncompliance (as failure to follow any applicable regulation or institutional policies that govern human subjects' research) and/or serious noncompliance (as noncompliance that materially increases risks that result in substantial harm to subjects or others, or that materially compromises the rights or welfare of participants) according to any reporting obligation and local regulatory requirements.

7.8 Pregnancy Reporting

Irrespective of the treatment received by the subject/patient, any patient's partner pregnancy occurring during study treatment or during the 7 months following study drug discontinuation must be reported within 24 hours of investigator's knowledge of the event.

Pregnancies will be treated as SAEs and the investigator will complete a pregnancy form, and forward it to the sponsor according to the reporting instructions provided by MedSIR at the site initiation visit and filed in the Investigator's File.

The subject/patient will be asked to provide follow-up information on the outcome of the pregnancy, including premature termination should the case arise. Spontaneous miscarriage and congenital abnormalities will also be reported as SAEs.

The follow-up period will be deemed to have ended when the health status of the child has been determined at 12 months of the infant's life.

Additional follow up information on any INCMGA00012 (retifanlimab) exposed pregnancy and infant will be requested at specific time points (i.e., after having received the initial report, at the end of the second trimester, 2 weeks after the expected date of delivery, and at 3, 6, and 12 months of the infant's life).

Follow-up queries may be sent, asking for further information, if required for a comprehensive assessment of the case.

8 STATISTICAL CONSIDERATIONS AND ANALYSIS PLAN

8.1 Sample Size

A total of 18 patients with unresectable locally advanced or metastatic PsqCC will be enrolled into this trial.

8.2 Justification of Sample Size

This is a multicenter, open-label, single arm, phase II trial evaluating the efficacy and safety of INCMGA00012 (retifanlimab) in unresectable locally advanced or metastatic PSqCC. The defined primary endpoint is ORR.

In the single arm phase II trial VinCap (57) patients with locally advanced PSqCC were treated with vinflunine. The trial evaluated CBR and ORR after 4 cycles. The 45.5% and 27.3% of patients achieved clinical benefit and objective response, respectively. These data suggest that excluding an ORR $\leq 5\%$ while targeting the improvement of the ORR to $\geq 25\%$ would be an adequate approach to assess a new antineoplastic strategy in this patient population.

The sample size calculation is based on an exact binomial test. The clinical trial is designed to demonstrate an ORR of at least 25% and to exclude a rate of less than 5% ($p_0=0.05$, $p_1=0.25$, $\alpha =0.05$, $\beta=0.80$, A'hern's exact design). At least 3 responders (18.8%) among 16 evaluable patients will be adequate to justify the investigation of this strategy in further clinical trials. Considering a drop-out rate of 10%, a sample size of 18 patients will be needed to attain 80% power at nominal level of one-sided alpha of 0.05.

8.3 Analysis Sets

Full analysis and safety set.

The full analysis and safety set includes patients who receive at least one dose of study medication.

Per-protocol set

All patients that accomplish selection criteria, receive at least one drug exposure, and receive the protocol required study drug exposure and processing. Criteria for determining the “per protocol” (PP) group assignment would be established by the Steering Committee before the statistical analysis begins. This analysis will only occur if this set differs by $\geq 10\%$ from the full analysis set.

Exploratory analysis set

All patients with biomarker evaluable samples with the assay and alternative platforms that accomplish selection criteria and receive at least one drug exposure.

Analysis set schedule

Primary, secondary and irRECIST endpoints will be analyzed on the full analysis set, and per-protocol populations. Full analysis set will be considered the primary population for the analysis. Biomarker and correlation between biomarkers and clinical outcomes will be analyzed on exploratory analysis set. Safety analysis will be performed on the safety set.

The estimands for the study based on ICH E9 (R1) addendum will be fully described in the statistical analysis plan.

8.4 Statistical Plan

8.4.1 Primary Efficacy Endpoint

The primary efficacy endpoint for the present study is the ORR. The ORR is defined as the number of patients with CR and PR divided by the number of patients in the analysis set. Tumor response will be defined as best response based on local investigator's assessment according to RECIST criteria v.1.1.

8.4.2 Secondary Efficacy Endpoints

The secondary efficacy variables are CBR, DoR, PFS, OS, and maximum tumor shrinkage. For an exhaustive definition of efficacy endpoints, please refer to the **Section 6.4.2**.

8.4.3 Exploratory Endpoints

The exploratory endpoints are PFS, CBR, and ORR based on irRECIST (see **Section 2.3.1**) and predictive biomarkers (such as but not limited to PD-1, PD-L1, HIV status).

The objective of the exploratory analyses of irRECIST is the characterization of INCMGA00012 (retifanlimab) clinical activity. We will also compare RECIST and irRECIST criteria for evaluation of the clinical response.

The objective of the statistical analyses of biomarkers is the identification of those markers or combinations of markers which show best association with positive clinical outcome of the study treatment. We will measure the clinical efficacy of that analysis in terms of ORR, CBR, PFS and irPFS.

8.4.4 Analysis of Baseline and Demographic Variables

The demographics and baseline characteristics including disease history and prior therapy are summarized using descriptive statistics.

8.4.5 Decision Rules and Adjustment of Alpha in The Study

The study would be defined as positive at final analysis, if the ORR in the INCMGA00012 (retifanlimab) arm is statistically significantly better ($p < 0.05$) than expected under the null hypothesis ($H_0: \text{ORR} \leq 5\%$). Decisions will be based on exact binomial test.

For all secondary and exploratory tests, we will use two-sided p-values with $\alpha \leq 0.05$ level of significance. The p-values emerging from these analyses will not be interpreted in a confirmative sense; they will be considered of descriptive nature only.

8.4.6 Primary Efficacy Analysis

We will describe number and proportion of responders. We will estimate the ORR with the 95% Clopper-Pearson confidence intervals and the p-value with exact binomial test. Analysis will be performed on the full analysis and PP sets. ITT will be considered the primary set for the analysis.

8.4.7 Secondary Efficacy Outcomes

We will describe number and proportion of patients with clinical benefit and 6-month PFS. We will estimate the proportion with the 95% Pearson-Clopper confidence intervals. For time to event endpoints (PFS, OS, irPFS and DOR), we will use the Kaplan-Meier method. Number and proportion of events, median survival time and survival rates, with corresponding 95%CI, will be calculated in both arms. For continuous outcome (maximum tumor shrinkage) we will use statistics of central tendency (median with 95%CI) and dispersion [range and interquartile range]. We provide waterfall plots of maximum tumor shrinkage from baseline. The duration of response has also plotted with bar plots.

Analysis will be performed on the ITT, and PP sets. ITT will be considered the primary population for the analysis. For all tests, we will use two-sided p-values with $\alpha \leq 0.05$ level of significance.

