6.4.3 OS and PFS Definitions

OS is defined as the time from the date of first dose of study treatment until death by any cause or the last date the patient was known to be alive. Patients who are lost to follow-up and the patients who are alive at the date of data cut-off will be censored at the date the patient was last known alive.

PFS is defined as the time from the date of first dose of study treatment until the first documented PD based on RECIST v.1.1 or death due to any cause, whichever occurs first based on local investigator's assessment according to RECIST criteria v.1.1. Patients with no progression or death will be assessed until patient discontinues study treatment, so they will be censored at the date of their last evaluable imaging.

Finally, 6-months PFS rate is defined as the proportion of patients who are alive and progression-free at 6 months from the date of first dose of study treatment based on irRECIST criteria.

6.4.4 irRECIST

Immunotherapeutic agents such as INCMGA00012 (retifanlimab) may induce antitumor effects by potentiating endogenous cancer-specific immune responses. The response patterns observed with these compounds may be different to the typical time course of responses seen with classical cytotoxic agents and can manifest a clinical response after an initial increase in tumor burden or even the appearance of new lesions. Standard RECIST v.1.1 may, therefore, not provide a precise response assessment of immunotherapeutic agents such as INCMGA00012 (retifanlimab).

irRECIST is RECIST v.1.1 adapted to account for the unique tumor response seen with immunotherapeutic agents. In this way, in subjects who have initial evidence of radiological PD by RECIST v.1.1, it is at the discretion of the Investigator whether to continue a subject on study treatment until repeat imaging is obtained. Subjects may receive study treatment and tumor assessment should be repeated at least four weeks later in order to confirm PD by irRECIST. Any subject deemed clinically unstable should be discontinued from trial treatment at first radiologic evidence of PD and is not required to have repeat imaging for PD confirmation. Clinical stability is defined as the following:

- Absence of symptoms and signs indicating clinically significant PD, including worsening of laboratory values.
- No decline in ECOG performance status.
- Absence of rapid PD.

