Confidence intervals will be presented to one more decimal place than the raw data. A two-sided significance level of 5% will be used for confidence intervals.

For binary endpoints, the 95% confidence intervals (CIs) will be constructed based on an exact binary distribution.

The Kaplan-Meier method will be used to estimate the time to event function, the median of time to event and the 95% confidence interval of the same will be calculated. These confidence intervals will be calculated based on the Greenwood method. Number and proportion of events, median survival time and survival rates, with corresponding 95%CI will be calculated.

All scores and change from baseline will be summarized in terms of the number of observations, mean, standard deviation, 95%CI of mean, median, range and interquartile range. We will examine the residuals to assess model assumptions.

All report outputs will be produced using SAS® version 9.4 version in a secure and validated environment. All report outputs will be provided to the Sponsor in a single Microsoft Word document.

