 - o When there is no evaluable tumor assessments best overall response will be NE.
- Unconfirmed Objective Response Rate (ORR) is defined as the proportion of patients with best overall response of unconfirmed CR or unconfirmed PR.
- Unconfirmed Clinical Benefit Rate (CBR) is defined as the proportion of patients with best overall response of unconfirmed CR or unconfirmed PR or SD ≥ 12 w.
- Confirmed Objective Response Rate (ORR) is defined as the proportion of patients with best overall response of confirmed CR or confirmed PR.
- Confirmed Clinical Benefit Rate (CBR) is defined as the proportion of patients with best overall response of confirmed CR or confirmed PR or SD ≥ 12 w.
- PFS is defined as the time from start dose until death by any cause or objective tumor progression according to RECIST v.1.1 or clinical disease progression. Patients with no progression or death will be censored at the date of their last evaluable imaging previous 35 days after last dose administration date. Censoring rules are specified below:

Situation	Date of progression or censoring	Outcome
Progression documented between scheduled visits	Earliest of: 
 • Date of assessment by investigator (if progression is based on clinical criteria); or • Date of assessment showing new lesion (if progression is based on new lesion); 	Progressed

Situation	Date of progression or censoring	Outcome
	or • Date of last radiological assessment of measured lesions (if progression is based on increase in sum of measured lesions).	
Death before first progression disease (PD) assessment	Date of death.	Progressed
Death between adequate assessment visits	Date of death.	Progressed
No progression	Date of last radiological assessment of measured lesions.	Censored
Treatment discontinuation for undocumented progression	Date of last radiological assessment of measured lesions.	Censored
Treatment discontinuation for toxicity or other reason	Date of last radiological assessment of measured lesions.	Censored

- 6-months PFS rate is defined as the proportion of patients who are alive and progression-free at 6 months from the date of first dose of study treatment based on RECIST criteria.
- The Overall Survival (OS) is defined as the time from start dose until death from any cause. Patients with no death will be censored on the last available follow-up date.

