5.4.4 Secondary Efficacy Analysis

Secondary efficacy results will be reported for the FAS and PP set.

For binary endpoints, the number and proportion of patients with response with the 95% Pearson-Clopper CI will be calculated.

The time to event endpoints will be performed with maximum likelihood method (MLM) for exponential distribution test, at nominal level of 0.05. Number and percentage of events will be described. The median, 6-month, 1 and 2-year

survival rates and 95% confidence intervals will be provided based on exponential MLM and Kaplan-Meier method. Swimmer plots for time-to-event endpoints will be provided.

For continuous outcome (maximum tumor shrinkage) we will use statistics of central tendency (median with 95%CI) and dispersion (range and interquartile range). We will provide waterfall plots of maximum tumor shrinkage from baseline. The duration of response has also plotted with bar plots.

For all tests, we will use two-sided P-values with alpha=0.05 level of significance. P-values emerging from these analyses will not be interpreted in a confirmative sense; they will be considered of descriptive nature only.

Table 2. Secondary Efficacy Estimands

Estimand	Population	Variable	Intercurrent event strategy	Summary measure
Secondary 1	FAS set	PFS	
 - Patients with no progression or death will be censored at the date of their last evaluable imaging previous 35 days after last dose administration date. - If no post-baseline tumor assessment is available, patients will be censored at the date of treatment initiation + 1 day. - Data for patients with an event who missed two or more scheduled assessments immediately prior to the event will be censored at the last tumor assessment prior to the missed visits. 	
Kaplan-Meier plot, number and proportion of events, median survival time, 6 months, 1- and 2-year survival rates with corresponding 95% CI.
 
Swimmer plot will be provided.

Sensitivity 1 to Secondary 1	PP set	PFS	Same as above	Same as above

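### Six-month PFS is planned as an exact-interval proportion in the protocol and as Kaplan-Meier and exponential rates in the SAP, with no estimator designated; one protocol definition also uses the wrong response criteria

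*Protocol*

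**What the plan says.** **Estimator, protocol.** Section 8.4.7 groups 6-month PFS with clinical benefit: "We will describe number and proportion of patients with clinical benefit and 6-month PFS", followed by "We will estimate the proportion with the 95% Pearson-Clopper confidence intervals". The next sentence treats PFS itself as a time-to-event variable: "For time to event endpoints (PFS, OS, irPFS and DOR), we will use the Kaplan-Meier method". Survival rates with 95% intervals are promised there, but no time point is named.

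**Estimator, SAP.** Section 5.4.1.1 words the endpoint as a proportion: "6-months PFS rate is defined as the proportion of patients who are alive and progression-free at 6 months from the date of first dose". The PFS row of Table 2 in 5.4.4, however, lists a Kaplan-Meier plot with "median survival time, 6 months, 1- and 2-year survival rates with corresponding 95% CI". The text above that table adds a second model for the 6-month, 1-year and 2-year figures: "survival rates and 95% confidence intervals will be provided based on exponential MLM and Kaplan-Meier method". Table 4, which lists the binary outcomes for subgroup analysis, does not include 6-month PFS; Table 3, for time-to-event outcomes, asks for a 6-month rate. Section 5.7 lists two changes from the protocol: the wording of alpha, and time to response replacing time to progression. The 6-month PFS method is not among them.

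**Criteria.** Protocol 2.2.1 lists 6-month PFS as a secondary endpoint by RECIST v.1.1, and 2.3.1 lists an irRECIST version as exploratory. The only worded definition in the protocol, in 6.4.3, reads "at 6 months from the date of first dose of study treatment based on irRECIST criteria". SAP 5.4.1.1 and 5.4.1.2 define the RECIST and irRECIST versions separately.

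**Interval.** For Kaplan-Meier quantities, SAP 5.1 says "These confidence intervals will be calculated based on the Greenwood method" and names no transformation.

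**The concern.** A named secondary endpoint can be reported as three different numbers, and nothing fixed in advance says which one counts. The three agree only in special cases. The proportion needs every patient's status at 6 months, and the plan's own rules leave some patients without one:

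- SAP 5.4.1.1 censors PFS at the last evaluable imaging before 35 days after the last dose, so a patient who stops for toxicity or another reason without progression can be censored early.
- Withdrawal and loss to follow-up censor at the last scan.
- Table 2 censors events that follow two or more missed assessments.

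Neither document says how such a patient enters the proportion. The non-responder rule in protocol 8.6 names ORR and CBR only. The choice could therefore be made after the data are seen.

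The criteria conflict is a separate fault. Read alone, protocol 6.4.3 turns a RECIST v.1.1 secondary endpoint into the irRECIST one that the same protocol calls exploratory.

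**Working it through.** The documents state no expected value, power or loss rate for 6-month PFS, so there is no planned figure to reproduce. The inputs they do give are N = 18 (protocol 8.1), scans every 8 weeks for 6 months and then every 12 weeks (protocol 6.4.1), and a 10% drop-out allowance made for ORR (protocol 8.2). I read the scans as weeks 8, 16, 24 and 36; 6 months is 6 × 30.4375/7 = 26.1 weeks.

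**Step 1. One patient.** If an early-censored patient stays in the denominator and is not counted as progression-free, the proportion falls by 1/18 = 5.6 points.

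**Step 2. Hypothetical data set.** Eighteen patients; 5 events at week 8, 3 at week 16, 1 at week 24; two of the other nine censored early.

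- Kaplan-Meier, both censored just after week 8: (13/18) × (8/11) × (7/8) = 46.0%.
- Kaplan-Meier, both censored just after week 16: (13/18) × (10/13) × (7/8) = 48.6%.
- Proportion: 7/18 = 38.9% (Clopper-Pearson 17.3% to 64.3%).
- With nobody censored, both methods give 9/18 = 50.0%.

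**Step 3. Expected size.** Assumptions, none from the documents: exponential PFS with a median of m months; progression recorded at the next scan; random exponential loss; censoring at the last scan before loss. The rate that the scan schedule can show at 6 months is the probability of no progression by week 24 (5.52 months):

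S = 2^(−5.52/m) = 14.8%, 27.9%, 38.4% for m = 2, 3, 4.

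To be known progression-free at week 26, a patient must also not be lost before the week-36 scan (8.28 months). So the expected proportion is S × R, where R is the chance of not being lost by then:

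- 10% lost by 6 months: R = 0.9^(8.28/6) = 0.865
- 3% per month: R = exp(−0.03 × 8.28) = 0.780
- 6% per month: R = exp(−0.06 × 8.28) = 0.608

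| Median PFS | S | 10% by 6 months | 3% per month | 6% per month |
|---|---|---|---|---|
| 2 months | 14.8% | 12.8% (−2.0) | 11.5% (−3.2) | 9.0% (−5.8) |
| 3 months | 27.9% | 24.2% (−3.8) | 21.8% (−6.1) | 17.0% (−10.9) |
| 4 months | 38.4% | 33.2% (−5.2) | 30.0% (−8.4) | 23.4% (−15.0) |

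A simulation of 20,000 trials of 18 patients per cell agreed with these figures to within 0.1 to 0.2 points. Kaplan-Meier averaged 14.7% to 14.9%, 27.9% to 28.0% and 38.4%, which shows no bias under random loss.

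**Step 4. How often the week-24 to week-36 gap matters.** The expected number censored at week 24 is 18 × S × (chance of loss between weeks 24 and 36). The smallest cell is 18 × 0.148 × (0.908 − 0.865) = 0.1 patients; the largest is 18 × 0.384 × (0.718 − 0.608) = 0.8.

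**Step 5. Interval form.** Take 3 of 18 progression-free with no censoring: estimate 0.167, Greenwood standard error √(0.167 × 0.833/18) = 0.088. The untransformed interval is 0.167 ± 1.96 × 0.088 = −0.5% to 33.9%. With the log-log transformation and the same Greenwood variance it is 4.1% to 36.5%. The transformation therefore has to be named.

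**The case against.** The strongest reply is that the SAP has already settled most of this. It puts the 6-month rate in its time-to-event rows for PFS and irPFS, leaves it out of its binary-outcome table, and defines the RECIST and irRECIST versions separately. On that reading, only two protocol sentences need tidying, and the endpoint is descriptive anyway. Much of this stands, and it is why the point is minor. It does not close the matter: the SAP keeps the proportion wording in 5.4.1.1, offers two models for the rate without ranking them, and does not record the protocol's exact-interval analysis as replaced.

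Several stronger readings are tempting and are not supported:

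- *Censored patients are counted as failures.* No section says so. It follows only if they stay in the denominator as not known to be progression-free.
- *They are carried forward as successes.* SAP 5.4.5 first assigns timed endpoints to Kaplan-Meier with withdrawals censored, and applies last observation carried forward only to the other variables. That points away from this reading.
- *The scan gap makes unknown status common.* A patient with a clean week-36 scan is classifiable. Step 4 gives 0.1 to 0.8 of 18 patients. With follow-up of 12 months after the last patient starts, administrative censoring before 6 months is not expected unless the trial stops early.
- *The SAP prescribes an untransformed interval.* Greenwood is a variance formula that log-log intervals also use; the SAP is silent on the transformation.
- *Gaps in the Table 2 numbering show a lost 6-month PFS analysis.* The gaps do not show what, if anything, was removed, and the PFS row already carries the rate.
- *The result will be reported on the wrong criteria.* The SAP has both definitions right; the conflict is confined to the protocol.

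The larger biases also rest on loss well above the one figure that the documents give. At 3% and 6% per month, 1 − exp(−0.18) = 16.5% and 1 − exp(−0.36) = 30.2% are lost by 6 months, against a 10% allowance. At 10%, the bias is less than one patient's weight of 5.6 points.

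**Conclusion.** The point holds as an inconsistency in both documents. The protocol states a simple proportion with an exact interval, the SAP states two model-based rates, and no text says which is the endpoint. The proportion is a poor choice whenever anyone is censored before 6 months. Coded with such patients as not progression-free, it is about 2 to 5 points low if 10% are lost by 6 months and 3 to 15 points low at 3% to 6% loss per month. These sizes assume exponential PFS with a median of 2 to 4 months and random loss, and are ranges, not forecasts. Kaplan-Meier is unbiased under the same conditions, but not if loss is related to prognosis. With no early censoring, the proportion and Kaplan-Meier coincide.

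The irRECIST wording in protocol 6.4.3 contradicts 2.2.1 and 2.3.1 and needs correcting whichever estimator is chosen.

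Severity is minor: secondary results are declared descriptive in protocol 8.4.5 and SAP 5.4.3, and the ORR decision does not depend on this endpoint.

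**What to change.** - Protocol 8.4.7: take 6-month PFS out of the Clopper-Pearson sentence.
- Both documents: name the Kaplan-Meier PFS rate at 6 months, by RECIST v.1.1 in the full analysis set, as the secondary estimate. Label the exponential estimate in SAP 5.4.4 as supportive only.
- SAP 5.4.1.1: reword the proportion definition as the Kaplan-Meier probability at 6 months, and record the change in 5.7.
- Protocol 6.4.3: change the criteria to RECIST v.1.1. Keep the irRECIST rate as exploratory, estimated by the same method.
- SAP 5.1: name the interval transformation, for example log-log.

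If the sponsor still wants a proportion, the text must say how a patient censored before 6 months counts in it. The cost is wording in two documents; no extra data are needed, and the estimates are standard software output.
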